	
Part 2: Expansion Phase
 
Once the Recommended Therapeutic Dose has been determined in Part 1 (a), a minimum of 150 patients will be enrolled in to the Expansion Phase, which is split into 3 periods. For participants taking part in the Dose Finding Phase (Part 1), eligibility criteria will be reassessed prior to entering Part 2 of the trial.
 
1) Baseline visit
 
In a minimum of 50 participants the following will be performed:
 

• Administration of a test dose of RESP301, at the RTD

• Assesses response to RESP301 (incl. recording any AEs, FEV1 pre- and post dose and monitoring methaemoglobin levels pre-, during and post- administration, using fingertip sensor; methaemoglobin level should be <=2% before, <=5% during, and <=3% at 30-60 mins post dose (i.e. if still >3% at 30 mins, check again at 60mins post dose).

 
During the visit participants who satisfactorily tolerate the test dose will then be enrolled into the “dormant period” of the study for 12 months.
 
An independent Data Monitoring Committee will review the data from the 50 participants that received the RTD. Based on the data from these participants, it will be decided whether test doses should be administered to further participants before enrolling them into the Dormant Period.
 
2) Dormant Period
 
Dormant period patients are requested at the baseline visit, and monthly follow-up calls, to inform the study team if they develop exacerbation symptoms indicative of a respiratory infection. There will be no other study procedures or data collection during the “dormant study phase” unless the participant experiences exacerbation symptoms.
 
3) Treatment Period
 
A patient who experiences exacerbation symptoms for at least 24 hours should contact the study team as soon as practicable to allow a study interaction to be undertaken remotely (via video link, if possible), within 72 hours of onset of at least one of the following: fever (<math>>38.0^{\circ}\text{C}</math>), systemic malaise, increased cough or wheeze, increased sputum volume or increased purulence. During the remote visit the patient’s symptoms will be discussed and if

--	--

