	
To be evaluated on the full cohort, and separately in the sub-cohort of those who test positive for SARS-CoV-2:
 

• Safety and tolerability of RESP301 in terms of:

○ % of participants able to tolerate the test dose in Parts 1(a), 1 (b) and 2

○ Total counts and cumulative incidence of:

▪ Adverse Events (AEs)

▪ Serious Adverse Events (SAEs)

▪ Suspected Unexpected Serious Adverse Reactions (SUSARs)

▪ Severe AEs

▪ Treatment-related AEs/SAEs

• Feasibility in terms of percentage of patients who, having experienced and correctly reported an exacerbation, receive the treatment within 48 hours of reporting their exacerbation

• Efficacy of RESP301 in terms of:

○ % of participants recovered by Day 7 and Day 14 post starting treatment

○ time to recovery (days until patient feels all their symptoms are back to their usual baseline (all VAS = 0))

○ preventing exacerbation-related hospitalisation and/or death

○ change in CCQ score

Duration of participation in the study	The overall study duration for each participant will be at most approximately 60 weeks, including one or more visits at a study centre in Parts 1/2, monthly follow-up calls, and, for those who experience an exacerbation, one week of treatment and additional monitoring calls at the beginning, during and following the treatment period.
Study population	Participants will be adult patients with spirometry-confirmed COPD or computerised tomography (CT) proven bronchiectasis, recruited from secondary and primary care sites in the UK.
Sample size	
Part 1(a):
 
We aim to recruit up to 48 participants. All participants who complete Part 1a, will also be eligible to enter Part 2 of the trial.
 
Part 1(b):
 
We aim to recruit 8 participants who are not experiencing an exacerbation. These participants will receive a short acting

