### **Part 2: Expansion Phase**

#### **Baseline Visit**

Once the RTD has been established in Part 1, [redacted]

- [redacted]
- [redacted]

During the visit participants who satisfactorily tolerate the test dose will be enrolled into the “dormant period”.

All patients including those receiving the test dose will undergo the following procedures

- Informed consent
- Inclusion and exclusion criteria
- Any medical assessments (e.g. heart or lung examination) which in the PI's opinion are required to assess whether the patient is suitable for the trial
- Demographic information
- Medical history and concurrent medications
- Height and weight
- Vital signs
- Pulmonary function tests (FEV1, FVC and % predicted), if required

Subjects that participate in Part 1 and do not meet any of the individual stopping criteria can enrol in Part 2. Eligibility criteria will be reassessed prior to entering Part 2 of the trial. Participants who have not satisfied inclusion/exclusion criteria will be excluded from continuing in the study.

An independent Data Monitoring Committee will review the data from the [REDACTED] participants that received RTD. Based on the data from these participants, it will be decided whether test doses should be administered to further participants for the remaining duration of the study.

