100295

100296

100297

100298

100299

100300

100301

100302

100303

100304

100305

100306

100307

100308

100309

100310

100311

100312

100313

100314

100315

100316

100317

100318

100319

100320

100321

100322

100323

100324

100325

100326

100327

100328

100329

100330

100331

100332

100333

100334

100335

100336

100337

100338

100339

100340

100341

100342

100343

100344

100345

100346

100347

100348

100349

100350

100351

100352

100353

100354

100355

100356

100357

100358

100359

100360

100361

100362

100363

100364

100365

100366

100367

100368

100369

100370

100371

100372

100373

100374

100375

100376

100377

100378

100379

100380

100381

100382

100383

100384

100385

100386

100387

100388

100389

100390

100391

100392

100393

100394

100395

100396

100397

100398

100399

100400

100401

100402

100403

100404

100405

100406

100407

100408

100409

100410

100411

100412

100413

100414

100415

100416

In Part 1, participants who do not meet any of the Individual Stopping Criteria (Section 7.7.2), and are suitable in the Investigator's opinion to proceed, can proceed to the next cohort (subject to SAC review).

In Part 2, participants who satisfactorily tolerate the test dose based on the above assessments, and are suitable in the Investigator's opinion to proceed, will be enrolled into the dormant period of the study.

[figure not shown]
Participants who completed the Screening visit and test dose but were not suitable to continue to the dormant period, should be followed up with a phone call 7 [REDACTED]

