## 10 Statistical Considerations

### 10.1 Statistical Hypothesis

Since this is an open label non-randomised study where the primary objective is to assess feasibility, no formal statistical analysis will be performed.

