# **3. EFFICACY AND SAFETY VARIABLES**

## **3.1 Efficacy**

The primary objective in part 1 (Dose Finding Phase) is to determine the maximum tolerable dose (MTD) and the recommended therapeutic dose (RTD) of the single agent RESP301. For these decisions individual and cohort stopping criteria were defined, see section 7.7.2 and 7.7.3 of the protocol. In a Safety Advisory Committee (SAC) meeting prior to part 2 of this study these doses will be determined. Hence no single primary and/or secondary endpoint for part 1 was defined.

In part 2 (Expansion Phase), the primary endpoints are:

- Percentage of patients entering the dormant period who, having experienced and correctly reported an exacerbation, commence self-administration of the treatment at home on the day the treatment is delivered.
- Percentage of patients who, having experienced and correctly reported an exacerbation, receive the treatment within 48 hours of reporting their exacerbation.
- Compliance with RESP301 administration schedule over the treatment period: for those participants commencing treatment, the percentage of total doses taken.

The secondary endpoints, which will be analyzed by treatment dose and separately in the sub-group of patients who had a positive test result for SARS-CoV-2 are defined as:

- % of participants able to tolerate the test dose in Part 1(a), Part 1(b) and Part 2, i.e. able to complete the test dose without any of the following:
  - o Troublesome cough, chest pain or tightness, bronchospasm or dyspnea that is deemed unacceptable by the patient.
  - o methemoglobin >5% during or >3% post dose (30 or 60 mins)
  - o any treatment-related AE that led to participant not being able to complete the test dose, and/or be suitable to be enrolled into the dormant period in the Investigator's opinion
  - o for the first 50 patients who will undergo pre and post-test dose spirometry, >20% reduction in FEV1 from pre-test dose to post

---

test at 60 min dose with symptoms listed above (patients with >20% reduction in FEV1 without symptoms would be offered the option to continue in the study).

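### The SAP commits its SARS-CoV-2-positive split only to test-dose tolerability, which is measured before the treated infection and is, in Part 2, either 100% by selection or missing

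*SAP*

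**What the plan says.** **Protocol.** The synopsis (Endpoints) requires all secondary endpoints to be evaluated in the full cohort and again in those positive for SARS-CoV-2. They are the percentage "of participants able to tolerate the test dose in Parts 1(a), 1 (b) and 2", adverse events by type, receipt of treatment within 48 hours, and efficacy (recovery by Day 7 and Day 14, time to recovery, exacerbation-related hospitalisation or death, CCQ change). Section 10.4.3 repeats the sub-cohort requirement for safety, tolerability and efficacy.

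**SAP.** Section 3.1 says the secondary endpoints will be "analyzed by treatment dose and separately in the sub-group of patients who had a positive test result for SARS-CoV-2". The only endpoint that follows is the percentage "of participants able to tolerate the test dose in Part 1(a), Part 1(b) and Part 2". In the same section 48-hour receipt becomes a primary endpoint, and the recovery, hospitalisation and CCQ endpoints are not listed. Section 5.11 summarises adverse events by treatment group and overall. Section 5.10 allows summaries for unspecified sub-groups if numbers permit, and Table 1.5 in Section 15.2 is provided for them, if any.

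**Route to a positive result.** In Part 2, the synopsis says "participants who satisfactorily tolerate the test dose will then be enrolled into the" dormant period, and Protocol 8.1.6 likewise refers to "participants who satisfactorily tolerate the test dose based on the above assessments". For Part 1, Protocol 5.1 says: "Subjects that participate in Part 1 and do not meet any of the individual stopping criteria can enrol in Part 2". Of the dormant phase the synopsis says "There will be no other study procedures or data collection during the" phase unless exacerbation symptoms occur. COVID-19 results are collected at the daily treatment calls and the two follow-up calls (synopsis; Protocol 5.1 and 8.5).

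**The concern.** The protocol asks how RESP301 performs in people with confirmed SARS-CoV-2 infection. The SAP's one committed answer uses a dose given at baseline, with a dormant period of up to 12 months between it and the treated infection. It also conditions an earlier outcome on a later event that, in Part 2, test-dose failures do not go on to reach.

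The gate is even written into the endpoint. SAP 3.1 counts as intolerance a treatment-related event that makes the participant unsuitable for the dormant period in the investigator's opinion.

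A clinical study report could therefore show complete tolerability in SARS-CoV-2-positive patients, when the figure reflects who was allowed to continue. The informative data, the home course during infection, have no committed sub-cohort output. The SAP flags that its full analysis set differs from the protocol's ITT population (5.2), but it does not say that it has narrowed the sub-cohort analysis.

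**Working it through.** **The plan's own figures.** There is no power calculation to reproduce; Protocol 10.1 states that "no formal statistical analysis will be performed". SAP 4 expects 30 of 150 to exacerbate: 30/150 = 20%, with no inputs given.

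**Step 1: selection.** Suppose 10 of the first 50 fail the test dose (illustrative).
- Full cohort: 40/50 = 80%.
- Only the 40 who passed can become dormant, be treated and then test positive. If n of them do, the sub-group shows n/n = 100%.

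An asymptomatic FEV1 fall above 20% is no exception, because SAP 3.1 does not count it as intolerance.

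**Step 2: missing values.** The synopsis recruits a further 100 with or without a test dose, and SAP 4 waives it if the first 50 show that this is safe. With a waiver, 100 of 150 have no test-dose value. If the dormant period is filled to 150 after 10 failures, 150 − 40 = 110 have none.

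**Step 3: how many positives would have a value.** Assumptions: test dose waived after the first 50, dormant period filled to 150, 20% treated, Part 1 entrants ignored. Let p be the probability of tolerating the test dose and q the positive share of those treated. The documents give neither.
- Expected positives = 30q.
- Expected positives with a test-dose value = 30q × 50p/150 = 10pq.
- Chance that none has a value = (1 − 0.2pq)^50.

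| p | q | Positives | With a value | Full cohort | Sub-group | Chance of none |
|---|---|---|---|---|---|---|
| 60% | 10% | 3.0 | 0.6 | 60% | 100% | 55% |
| 60% | 25% | 7.5 | 1.5 | 60% | 100% | 22% |
| 80% | 10% | 3.0 | 0.8 | 80% | 100% | 45% |
| 80% | 25% | 7.5 | 2.0 | 80% | 100% | 13% |
| 90% | 10% | 3.0 | 0.9 | 90% | 100% | 40% |
| 90% | 25% | 7.5 | 2.25 | 90% | 100% | 10% |

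A simulation of 20,000 trials per row agreed with the last column to within half a percentage point. The sub-group figure was 100% in every simulated trial that had one. Over p from 60% to 100% and q from 5% to 50%, the number with a value runs from 10 × 0.6 × 0.05 = 0.3 to 10 × 1.0 × 0.5 = 5.

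**Step 4: treatment-period endpoints instead.** All treated positives could then contribute: 30 × 5% = 1.5 to 30 × 50% = 15, or 3 to 9 for q of 10-30%.

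**Step 5: does it depend on 30 treated?** The protocol calls 30 a minimum. If the background rate of 0.85 exacerbations per person in moderate COPD is read as an annual Poisson rate (an assumption), 1 − e^(−0.85) = 57%, about 86 of 150. Counts rise, but each value is still 100% or missing.

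**The case against.** A reader might infer that every SARS-CoV-2-positive participant must have passed the test dose and that the sub-group is 100% under any reading. The documents do not support that.

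- **Waived test doses.** Up to 100 of 150 may have no test dose. Their value is missing. This stands, and it makes the row less usable.
- **No window for a positive result.** SAP 3.1 asks only for a positive result, undated. One in the medical history, or reported at the Day 7 call to a participant who did not continue (SAP Table 3, footnote 1), could admit a non-tolerator. For the same reason one cannot state as fact that no test dose was taken while infected; the schedules show no SARS-CoV-2 test at dosing visits.
- **Part 1 entry.** Protocol 5.1 admits to Part 2 those who met no individual stopping criterion, while the synopsis (Sample size) makes all Part 1a completers eligible. The criteria in Protocol 7.7.2 are not visible, so whether meeting none equals tolerating the dose under SAP 3.1 cannot be checked.

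A reader might also infer that the sub-cohort objective is abandoned. That is too strong. Protocol 10.4.3 still commits to it, and SAP 5.10 permits sub-group summaries of primary and secondary endpoints, which would include compliance and 48-hour receipt. But those are optional and do not name SARS-CoV-2, so the accurate statement is that the SAP commits no such analysis.

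Finally, the study is descriptive, the endpoint's label does say test dose, and no decision is tied to this row. That limits the consequence but does not make the row informative.

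**Conclusion.** The point holds in this form. The only endpoint that SAP 3.1 places under the SARS-CoV-2 split is measured before the treated exacerbation. For test-dosed Part 2 participants who test positive around that exacerbation it is 100% by selection; for those whose test dose was waived it is missing. It cannot inform on tolerability during infection. The protocol's sub-cohort evaluation of adverse events, 48-hour receipt and efficacy has no committed SAP output.

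The selection result needs no assumption about p or q. It does require that a positive means one reported around the treated exacerbation, which the SAP leaves undefined, and it is not claimed for Part 1 entrants. The counts (about 0.8 evaluable of 3 positives at p = 80% and q = 10%) rest on assumed p and q, 30 treated, and a waiver after the first 50.

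This concerns a secondary, descriptive objective. It should be corrected because the misreading is easy to foresee and the correction is modest.

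**What to change.** Change the SAP only.

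1. Do not present test-dose tolerability by SARS-CoV-2 status. Alternatively, keep the row and label it as measured before infection and in a selected group. If the split is dropped for this endpoint, record that as a departure from the protocol synopsis.
2. Apply the split to treatment-period outcomes: AEs and SAEs with onset from the first home dose to Day 28 after end of treatment, compliance, 48-hour receipt, and the protocol's recovery, hospitalisation/death and CCQ endpoints. The efficacy endpoints must first be added to SAP 3.1 and the table list.
3. Define the sub-group as treated participants with a positive result reported for the treated exacerbation, from symptom onset to a stated cut-off. Use the date of the reporting call where no sample date exists.
4. Show treated-negative and treated-untested separately. Testing follows prevailing NHS guidance and results are recorded if available, so untested must not be read as negative.

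**Cost.** SAP wording and a few more outputs. The endpoints are already in the protocol, and COVID-19 results are already collected at the calls. The sub-group stays small, about 3 to 9 people if 10-30% of 30 treated are positive. With 4 events in 8 people, for instance, the exact 95% interval runs from 16% to 84%, so a listing may serve better than tables.

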### **3.2 Safety variables**

The safety end-points for this study are:

- Adverse Events (AEs)
- Serious Adverse Events (SAEs)
- Suspected Unexpected Serious Adverse Reactions (SUSARs)
- Severe AEs
- Treatment-related AEs/SAEs Adverse events (AEs) and serious adverse events (SAEs)

## **4. SAMPLE SIZE JUSTIFICATION**

The primary objective of this study is to determine the MTD and RTD of RESP301 and to assess feasibility. No formal sample size calculation was performed. In Part 1, we aim to recruit up to 56 participants (8 per dose group) to receive one dose of RESP301 (alone or in combination).

In Part 2, we aim to recruit around 150 patients from secondary care and primary care sites in the UK into the dormant period. The first 50 consented participants will receive an initial test dose of RESP301 before progressing to the dormant period. If, based on the first 50 participants, the DMC determines that it is safe to do so, the remaining consenting participants will not be required to receive a test dose before progressing to the dormant period. It is estimated that over 12 months, 30 of the 150 enrolled participants will exacerbate. These participants will commence self-administered RESP301 treatment. Non-exacerbating participants will receive no further study interventions.

## **5. METHODS OF ANALYSIS AND PRESENTATION**

### **5.1 General Principles**

The statistical analysis will be performed using the validated software package SAS version 9.4 or higher (SAS Institute Inc., Cary, NC 27513, USA).

All recorded and derived variables will be presented by treatment group and visits (if appropriate) using descriptive summary tables (continuous data: sample size, mean, standard deviation (SD), minimum, median, maximum; categorical data: sample size, absolute and relative frequency).

The mean and median will be presented to one more decimal place than the raw data. The SD will be presented to two more decimal places than the raw data. The percentages will be presented to 1 decimal place. In all the summaries, the treatment groups will be displayed in the following order: part 1 (RESP301 1 ml, 2 ml, ...6 ml, RESP+Vent 6 ml) and then part 2.

For all parameters, baseline is defined as the last available pre-treatment value (i.e. the last non-missing value available before study drug administration. In general, missing data will be treated as missing and no attempts will be made to impute values for missing data.

No formal interim efficacy analyses are planned in this study; however, several safety interim analyses by the Safety Advisory Committee (SAC) will be performed as detailed in the protocol, see section 7.7 for part 1 and an Independent Data Monitoring Committee (IDMC) will review the safety data on an ongoing basis as described in the DMC charter, see section 10.6 of the protocol.

Subjects who did not receive any study medication (screening failures) will be listed separately and not presented in any table or figure, except in the patient's disposition table.

The versions of the following international dictionaries (MedDRA version 26.1 and WHO DD, version 2024) will be used for medical coding:

Adverse events: Medical Dictionary for Regulatory Activities (MedDRA).

Medical Histories: Medical Dictionary for Regulatory Activities (MedDRA).

Medications: World Health Organization (WHO) Drug Dictionary including Anatomical Therapeutic and Chemical (ATC) classification.

If a medication in the drug dictionary (DD) table is associated with more than one ATC code, the first ATC code will be assigned to that medication.

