**Table 1: Treatment Groups**

Part	Treatment group*	Label	Short label**
1	1 (N=8)	RESP301 1 ml	1ml
	2 (N=8)	RESP301 2 ml	2ml
	3 (N=8)	RESP301 3 ml	3ml
	4 (N=8)	RESP301 4 ml	4ml
	5 (N=8)	RESP301 5 ml	5ml
	6 (N=8)	RESP301 6 ml	6ml
	7 (N=8)	RESP+Vent 6 ml	R+V
2	8 (N=150)	RESP301 RTD	RTD

\* During a meeting on the 11th of January 2022 it was decided that the RTD dose is 4 ml and the MTD dose 6 ml.

\*\* Short labels may be used due to paper space requirements.

RESP301 is prepared by mixing two sterile solutions (one of NaNO2/mannitol and one of citric acid buffered to pH █) in the nebulizer. The solution is to be nebulized within 5 minutes post mixing as per the instructions given in the SoA. The inhalation of the medication should start within 5 minutes of mixing the solutions and the inhalation process should be complete within 20 minutes of starting inhalation.

An overview of the study procedures is provided in table 2 below for part 1 of the study and in table 3 for part 2, see protocol page 51, table 8-1:

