## **5.10 Analysis of Efficacy Variables**

All primary and secondary efficacy parameters, see section 3, will be summarized descriptively and no formal statistical analyses will be performed. The analyses will be performed by treatment group and overall, for both the FAS and PPS set using appropriate descriptive statistics. The results of the spirometry will also be presented over time, i.e. baseline, 30-, 60- and 90-minutes post baseline.

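### Feasibility and tolerability proportions from groups of 8, 50 and about 30 are planned as N, n and % with no confidence interval, so an estimation-only study would report no precision

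*SAP*

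**What the plan says.** SAP section 5.1 lists the statistics to be produced. For binary and other categorical variables they are "categorical data: sample size, absolute and relative frequency", with percentages to one decimal place. For continuous variables they are "continuous data: sample size, mean, standard deviation (SD), minimum, median, maximum". SAP section 5.10 states that all primary and secondary efficacy parameters "will be summarized descriptively and no formal statistical analyses will be performed", by treatment group and overall.

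The endpoints affected are in SAP section 3.1:

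- the percentage who start self-administration on the day treatment is delivered (Part 2)
- the percentage who receive treatment within 48 hours of reporting an exacerbation (Part 2)
- the percentage of total doses taken by those who start treatment (Part 2)
- the percentage able to tolerate the test dose in Parts 1(a), 1(b) and 2. Protocol section 10.4.2 makes tolerability at each dose level the Part 1 primary endpoint.

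On numbers, SAP section 4 says "No formal sample size calculation was performed". It plans 8 participants per Part 1 group, up to 56 in all. For Part 2 it says "The first 50 consented participants will receive an initial test dose of RESP301 before progressing to the dormant period" and "It is estimated that over 12 months, 30 of the 150 enrolled participants will exacerbate".

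The abbreviation lists of both documents include the term confidence interval. No SAP analysis section or table title uses it, nor does any protocol text that can be read.

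**The concern.** This is a single-arm study with no comparator, no hypothesis test and no formal basis for its size. In Part 2, what it yields is a set of estimated proportions. If the programmer follows section 5.1 as written, a table will show an entry such as 8/8 (100.0%) or 24/30 (80.0%) and stop there. The denominator is visible, but most readers cannot work out from it how wide a range of true rates the data allow.

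What is at stake is interpretation of the final report: how firmly it can say that home self-administration is feasible and that a single dose is tolerated. The SARS-CoV-2-positive sub-group, which the SAP analyses separately, will be smaller still.

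**Working it through.** **Inputs.** Part 1 group size 8, in seven groups (SAP Table 1 and section 4). Part 2 test-dose group 50 (SAP section 4). Expected number treated in Part 2: 30 of 150 (SAP section 4). The documents give no confidence level or interval method, so I assume two-sided 95% exact (Clopper-Pearson) limits and show alternatives.

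**The plan's own figures.** 7 × 8 = 56 reproduces the Part 1 total. 6 × 8 = 48 reproduces the protocol's Part 1(a) total. 30/150 = 20% is a stated estimate with no formula behind it. The documents state no precision figure to reproduce.

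**Formula.** For x successes in n, the lower limit is the 0.025 quantile of Beta(x, n − x + 1) and the upper limit is the 0.975 quantile of Beta(x + 1, n − x). When x = n, the lower limit reduces to 0.025^(1/n) and the upper limit is 100%.

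**Clean results.**

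- n = 8: 0.025^(1/8) = 63.1%, so the failure rate could be as high as 100 − 63.1 = 36.9%.
- n = 30: 0.025^(1/30) = 88.4%, failure rate up to 11.6%.
- n = 50: 0.025^(1/50) = 92.9%, failure rate up to 7.1%.

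**Other possible results (hypothetical outcomes, for illustration only).**

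| Result | % | Exact 95% CI |
|---|---|---|
| 7/8 | 87.5 | 47.3 to 99.7 |
| 6/8 | 75.0 | 34.9 to 96.8 |
| 27/30 | 90.0 | 73.5 to 97.9 |
| 24/30 | 80.0 | 61.4 to 92.3 |
| 15/30 | 50.0 | 31.3 to 68.7 |
| 45/50 | 90.0 | 78.2 to 96.7 |

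With 30 treated, the half-widths are (97.9 − 73.5)/2 = 12 points at 90%, (92.3 − 61.4)/2 = 15 points at 80% and (68.7 − 31.3)/2 = 19 points at 50%.

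**Sensitivity to method, for 8/8.** The Wilson lower limit is 67.6%, so failure up to 32.4%. A one-sided 95% exact limit is 0.05^(1/8) = 68.8%, so failure up to 31.2%. The size of the uncertainty does not depend on the choice of method.

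**Where a binomial interval does not apply.** Percentage of doses taken is a per-participant quantity summarised by mean and SD, so it needs a t or bootstrap interval. The documents give no SD, so I put no width on it.

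**Overlap between groups.** SAP section 2.2 lets one person enter more than one Part 1 group. Protocol sections 5.1 and 7.7.2 allow this only if no individual stopping criterion was met at an earlier dose. The groups are therefore neither independent nor equally selected. The 56 administrations are not 56 independent observations, and later groups may be enriched for people who tolerate the product.

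**The case against.** The best defence is that the documents are consistent. They describe a feasibility study with descriptive reporting, no testing and no sample size calculation, and they break no promise. N and n will be shown, so anyone can derive an exact interval. The reference in SAP section 5.10 to suitable descriptive statistics does not forbid one, and no readable success threshold exists to compare it with. Much of this stands, and it is why the point is a reporting improvement rather than an error. It does not remove the gap: section 5.1 spells out which statistics will be produced, and an interval is not among them. An interval is estimation, so it fits a plan without tests.

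Four stronger readings are tempting, and the documents do not support them:

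- **That results appear as bare percentages.** They do not. The sample size and the count accompany each one.
- **That the dose choice suffered.** Escalation followed a count of participants meeting stopping criteria, plus a rule on related serious events, with committee review (protocol synopsis). SAP Table 1 records that on 11 January 2022 "it was decided that the RTD dose is 4 ml and the MTD dose 6 ml". Intervals in the final tables could not have affected that.
- **That the test-dose waiver is unsupported.** The IDMC decides from its own review under a charter that is not among the documents. Nothing shows which statistics it uses.
- **That no interval is planned anywhere.** Protocol sections 10.2, 10.4.2 and 10.4.3 are partly redacted, so this can be said only of the SAP and the readable protocol text.

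**Conclusion.** The point holds as a minor, nearly free improvement. As written, the SAP yields no statement of precision for the proportions that make up the main Part 2 output or for tolerability in each group. The uncertainty is large enough to matter to a reader: 63% to 100% for 8 of 8, and about 12 to 19 points either side for observed proportions between 90% and 50% in 30 people.

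The 37% failure rate is the upper end of a two-sided 95% exact interval, not an estimate of the failure rate. The Part 2 widths assume that about 30 participants contribute, as the SAP expects; fewer would widen them. Each Part 1 interval describes the people admitted to that cohort, who may include some who had already tolerated an earlier dose. Overlapping or separate intervals across doses should not be read as evidence for or against a dose difference.

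**What to change.** Add to SAP section 5.1, with a cross-reference in 5.10, two-sided 95% Clopper-Pearson intervals for:

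- the proportion starting treatment on the delivery day
- the proportion receiving treatment within 48 hours
- test-dose tolerability within each Part 1 group and in the Part 2 test-dose group

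Add a t or bootstrap 95% interval for the mean percentage of doses taken, naming which one in advance.

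State that no binomial interval will be given for the pooled overall Part 1 column, and that the intervals are not for comparing doses, because participants can appear in several groups and are selected on having met no earlier stopping criterion. State also that the intervals are descriptive and no test is implied.

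The cost is a few lines of SAP text and one option in the table program. It needs no new data, no extra participants and no change to study conduct.
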